Study Protocol with Statistical Analysis Plan

Study Title: Effects of Salvinatorin A on Brain Function

Clinical Trials ID (NCT number): NCT03418714

Last Protocol Approval Date: October 5, 2018

This protocol will include two or more administrations of an inhaled dose of salvinorin A in experimental laboratory settings. The first experimental session will involve administration of a 15 µg/kg dose of salvinorin A without brain fMRI scanning. The first session will allow the participant to become familiar with the inhalation procedure as well as the dose of salvinorin A that they will encounter in the fMRI scanner. If the volunteer displays involuntary movement or no memory for the experience, we may repeat the drug administration at a lower dose (12 µg/kg). The final experimental session will involve inhalation of either 12 or 15 µg/kg salvinorin A during fMRI scanning. Our previous research has shown that both 12 and 15 µg/kg doses of salvinorin A are well tolerated in participants with history of hallucinogen use (Johnson et al., 2011; Johnson, MacLean, Caspers, Prisinzano, & Griffiths, 2016; MacLean, Johnson, Reissig, Prisinzano, & Griffiths, 2013; Maqueda et al., 2015).

The primary objective of this study is to investigate the effects of salvinorin A on human brain activity and connectivity. Secondary objectives include investigating the relationship between individual differences in subjective effects of salvinorin A and individual differences in brain response to salvinorin A.

Study Procedures

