First experimental session day: During the first drug administration session day, similar to our previous research with salvinorin A (Johnson et al., 2011; Johnson et al., 2016; MacLean et al., 2013), participants will be administered salvinorin A via inhalation while lying down. At least one staff member will be present in the room to directly monitor the participant for at least 45 minutes after each drug administration. Staff members will rate participant behavior and ask the participant to make verbal ratings of subjective effects at set time intervals throughout the drug administration session. In our previous research with salvinorin A, subjective effects resolved within 45 minutes (Johnson et al., 2011; Johnson et al., 2016; MacLean et al., 2013). Volunteers will complete several questionnaires and computer-based assessments approximately 45 minutes after each drug administration.

Study staff will record observations of subject movement during the acute effects of salvinorin A. Participants who are particularly sensitive to the effects of salvinorin A may exhibit involuntary movement of head, torso, or appendages, or resting or kinetic tremor. If a given participant exhibits gross involuntary movement or resting tremor after drug administration during the first experimental session, the study team will determine if this movement would invalidate MRI data collection. If the volunteer exhibits involuntary movement that would invalidate MRI data collection, or reports no memory for the experience, the session may be repeated with a 12 µg/kg dose of salvinorin A. Study volunteers will not advance to the MRI experimental session if it is determined that they have exhibited involuntary movement judged likely to invalidate MRI data collection at both 15 and 12 µg/kg.

Schedule of Events for First Experimental Session Day

Time Point (minutes from drug administration)	Procedure	Description
-30 (or more)	Intake procedures	Participant will complete drug and pregnancy urine tests, and complete a pre-session questionnaire to assess the psychological “set” of the volunteer
-10 (approximate)	Setup	The participant will be brought to the experimental session room, and the prepared salvinorin A dose for this participant will be brought to the session room from the BPRU pharmacy. All materials and equipment for drug delivery and study monitoring will be set up.
0	Drug administration	Participant will be administered salvinorin A via inhalation while lying down.

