1	Post drug-administration measurement	Participant will rate overall drug strength. Monitors will rate observed intensity of drug effect and amount of spontaneous speech and movement of the participant.
2	Post drug-administration measurement	Participant will rate overall drug strength. Monitors will rate observed intensity of drug effect and amount of spontaneous speech and movement of the participant.

3	Post drug-administration measurement	Participant will rate overall drug strength. Monitors will rate observed intensity of drug effect and amount of spontaneous speech and movement of the participant.
4	Post drug-administration measurement	Participant will rate overall drug strength. Monitors will rate observed intensity of drug effect and amount of spontaneous speech and movement of the participant.
5	Post drug-administration measurement	Participant will rate overall drug strength. Monitors will rate observed intensity of drug effect and amount of spontaneous speech and movement of the participant.
10	Post drug-administration measurement	Participant will rate overall drug strength. Monitors will rate observed intensity of drug effect and amount of spontaneous speech and movement of the participant.
15	Post drug-administration measurement	Participant will rate overall drug strength. Monitors will rate observed intensity of drug effect and amount of spontaneous speech and movement of the participant. Monitors will also complete the Fahn-Tolosa-Marin Tremor Rating Scale.
20	Post drug-administration measurement	Participant will rate overall drug strength. Monitors will rate observed intensity of drug effect and amount of spontaneous speech and movement of the participant.
25	Post drug-administration measurement	Participant will rate overall drug strength. Monitors will rate observed intensity of drug effect and amount of spontaneous speech and movement of the participant.
30	Post drug-administration measurement	Participant will rate overall drug strength. Monitors will rate observed intensity of drug effect and amount of spontaneous speech and movement of the participant. Monitors will also complete the Fahn-Tolosa-Marin Tremor Rating Scale.

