involve standard methods and established pulse sequences utilized in research evaluations and do not involve the injection of any contrast or other invasive procedures. We will work closely with the neuroimaging experts in the MRI Research Service Center to ensure safe and effective implementation of the tasks conducted in the scanner. [name], the principle investigator on the team, has extensive experience with brain imaging and is currently leading MRI and PET neuroimaging studies of the acute effects of the classic hallucinogen psilocybin. [name] will oversee the development and conduct of brain imaging procedures and analysis of the resulting data.

After completing the scanning procedures, the participant will complete brief (e.g., 10-15 minute) behavioral measures and/or questionnaires regarding the subjective effects that they experienced during the scanning session. These measures will be used along with ratings made in the scanner to interpret differences in brain activation between participants and across conditions. For example, changes in brain activation may be correlated with ratings of subjective effects (e.g. the Mystical Experience Questionnaire, or the Challenging Experience Questionnaire) experienced during the scanning procedures. Subjects will also be asked to write a narrative description of the experience of each salvinorin A session within about one week after a session.

Participants will undergo drug administration during collection of BOLD signal in the MRI. Real-time fMRI analysis techniques may be employed to monitor volunteer head motion as the scans are collected. If participants exhibit gross (> 1mm of movement in any plane) frequent (for more than 25% of the scan time) head motion, we may repeat the given drug administration and scan, since frequent gross motion may invalidate BOLD imaging data (Power, Barnes, Snyder, Schlaggar, & Petersen, 2012; Power et al., 2014). We may repeat drug administration and scanning up to two times. No more than one salvinorin A administration will occur on a single day. Repeated administrations of salvinorin A may occur on consecutive days.

Schedule of Events for Second Experimental Session Day

Time Point (minutes from drug administration)	Procedure	Description
-65 (or more)	Intake procedures	Participant will complete drug and pregnancy urine tests, and complete a pre-session questionnaire to assess the psychological “set” of the volunteer (including mood state and cognitive state)

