Using the lower (more conservative) of the two effect sizes from our previous psilocybin and salvinorin A studies ($d = 0.89$), and an alpha of 0.05, 6 volunteers would be sufficient to detect effects on ratings of drug intensity with 95% power. Empirical and simulation studies have provided recommendations for sample size of imaging experiments (Zandbelt et al., 2008). For similar parameters, including an effect size of 0.89, alpha of 0.05, and 80% power, 21 participants are necessary to power an ROI-based analysis of effects on brain activity similar to behavioral effects of psilocybin. Far fewer participants would be necessary to detect effects similar to the behavioral effects of salvinorin A, though no specific sample size recommendations were made by Zandbelt and colleagues for such a large effect size ($\eta^2 = 0.81$, equivalent to $d > 4$). Thus, the proposed study of 20 participants would be powered to detect clinically significant differences in brain activity between placebo and salvinorin A conditions. Given that consent will be obtained at the initial in-person screening interview, we are requesting approval to consent up to a total of 200 volunteers.

MRI data analyses: MRI data will be preprocessed using standard methods. The time course of brain regions in standard brain atlases (e.g. Chen Atlas or Power Atlas) will be extracted and submitted to functional connectivity analysis.

Statistical analysis of behavioral data: Baseline demographic data will be summarized with descriptive statistics to describe the volunteer population. For measures assessed at multiple time-points, including subjective effects ratings, both time-course and peak-effect data will be examined. For outcomes assessed at screening and one week after the final salvinorin A session, a paired t-test will be used to assess change from baseline (screening). Behavioral measures (including monitor ratings, subjective effects ratings, and questionnaire data) will be correlated with brain-imaging outcome measures to investigate the relationship between individual differences in subjective drug response and individual differences in neural drug response.

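### The brain-behaviour correlations specify no between-volunteer adjustment for head motion, so motion cannot be ruled out as a source of any association found.

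*Combined protocol and SAP*

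**What the plan says.** The opening section sets a secondary objective of "investigating the relationship between individual differences in subjective effects of salvinorin A and individual differences in brain response to salvinorin A". The analysis that serves it is in the Statistical analysis plan, under Statistical analysis of behavioral data: "Behavioral measures (including monitor ratings, subjective effects ratings, and questionnaire data) will be correlated with brain-imaging outcome measures". No covariate or partial correlation is named. Under MRI data analyses, preprocessing is left to standard methods, with no motion step listed.

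Three other places bear on this:

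- First experimental session day: "Participants who are particularly sensitive to the effects of salvinorin A may exhibit involuntary movement of head, torso, or appendages".
- Schedule of Events for First Experimental Session Day, repeated from 1 to 45 minutes: "Monitors will rate observed intensity of drug effect and amount of spontaneous speech and movement of the participant".
- Second experimental session day: a scan may be repeated after excessive head motion, "since frequent gross motion may invalidate BOLD imaging data".

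The plan also has motion safeguards. Volunteers whose first-session movement or resting tremor is judged likely to spoil the MRI do not advance (First experimental session day; Tremor Rating Scale entry under Study Statistics). In the scanner they are asked to keep still and the head is padded. Monitoring is optional: "Real-time fMRI analysis techniques may be employed to monitor volunteer head motion as the scans are collected". The repeat scan is also optional and has a threshold: "If participants exhibit gross (> 1mm of movement in any plane) frequent (for more than 25% of the scan time) head motion".

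**The concern.** The analysis compares volunteers with one another. If those who respond more strongly also move more, and motion distorts the imaging measure, the behavioural score and the imaging change will correlate with no neural link between them. The protocol itself raises both halves of that path as possibilities. One of the listed behavioural sources, the monitor ratings, includes movement as a scored item.

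Realignment or motion regression, if that is what standard methods means, acts within each scan. It does not remove differences between volunteers in the artefact that remains. An association produced this way would be read as a positive answer to the secondary objective. This is separate from the within-volunteer contrast of drug with inhaled air.

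**Working it through.** The plan gives no sample size, power or significance level for these correlations, so there is no stated figure to reproduce.

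**Inputs.** From the Sample size section: n = 20. From the Second experimental session day: 20-minute scans and a repeat threshold of more than 25% of scan time, so 0.25 × 20 = 5 minutes of motion above 1 mm can occur without reaching it. Assumed: a two-sided 5% test; a = correlation of motion with the behavioural score; b = correlation of motion with the imaging change. The documents give neither a nor b.

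**Critical values.** |r| = t/√(df + t²).
- Unadjusted, df = 18: 2.101/√(18 + 4.414) = 0.444.
- Adjusted for motion, df = 17: 2.110/√(17 + 4.452) = 0.456.

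**Bias.** With no true link, the expected correlation is a × b. The partial correlation is (r_xy − r_xm·r_ym)/√[(1 − r_xm²)(1 − r_ym²)], where x is the score, y the imaging change and m motion. Its population value is zero when m is measured without error. Simulation with 100,000 datasets per setting:

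| a | b | Expected r | Rejects, unadjusted | Rejects, adjusted |
|---|---|---|---|---|
| 0.3 | 0.3 | 0.09 | 6.6% | 5% |
| 0.5 | 0.5 | 0.25 | 19% | 5% |
| 0.7 | 0.7 | 0.49 | 62% | 5% |

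**Imperfect motion measurement.** At a = b = 0.7, the adjusted test rejects about 10% of the time if the motion summary has reliability 0.8, and about 21% at reliability 0.6.

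**Cost of adjusting.** Take a true r of 0.6, with motion a by-product of drug response (correlation a with the score) and no artefact. The partial correlation is then 0.6 × √[(1 − a²)/(1 − 0.36a²)].
- a = 0.5: 0.6 × √(0.75/0.91) = 0.545.
- a = 0.7: 0.6 × √(0.51/0.8236) = 0.472.

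Unadjusted Pearson power is about 84% throughout. Adjusted power is:

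| a | Pearson | Rank-based |
|---|---|---|
| 0 | 81% | 75% |
| 0.5 | 71% | 64% |
| 0.7 | 56% | 50% |

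**The case against.** The strongest reply is that the plan already takes motion seriously and that the bias may be slight. Volunteers who move badly are screened out, those scanned are padded and told to keep still, and a spoiled scan may be repeated. Dosing information and rationale reports no involuntary movement at 15 µg/kg in the prior studies; two volunteers in one of them moved, at doses above 15 µg/kg. All this points to the low end of the range, where the rejection rate is about 7% rather than 5%. That stands as a limit on size. It does not supply an adjustment, because the safeguards address gross motion at collection, several are discretionary, and none enters the analysis.

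A reader might infer four stronger things that the documents do not support:

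- That the plan has decided against adjustment. It specifies none; standard methods could include within-scan motion correction.
- That the monitor rating measures the scanner artefact directly. It is made in the first session, outside the scanner, and covers general movement. The second-day schedule lists no monitor rating, and the text there mentions in-scanner ratings without saying what they cover. The rating is at most an indirect marker.
- That the movement item will certainly be correlated. The plan says monitor ratings, which also cover observed intensity and an end-of-session questionnaire.
- That sensitive volunteers do move more. The protocol says only that they may.

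Adjustment is not free either. It can remove real signal if movement marks a stronger drug effect, and a noisy motion summary leaves some bias behind. Both points stand and shape the fix.

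**Conclusion.** The concern holds in a limited form. The analysis serving the secondary objective specifies no between-volunteer motion adjustment and does not exclude a movement-containing rating from its predictors, although the protocol names motion as a threat to BOLD data. An association found this way could not be told apart from one produced by motion.

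The size is uncertain. Over assumed a = b of 0.3 to 0.7 the false-positive rate runs from about 7% to 62%, and the protocol's safeguards and prior experience favour the lower part. The upper figures illustrate what strong motion correlations would do; they are not a forecast for this trial. All the rates assume n = 20, a nominal two-sided 5% test and linear relations. The change is worth making because it is cheap, but the adjusted result should inform interpretation, not decide it.

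**What to change.** Amend Statistical analysis of behavioral data as follows:

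1. Do not use the monitor speech/movement item as a predictor of neural drug response. Keep it as a description or as a negative control.
2. For each brain-behaviour correlation, also report a partial correlation adjusted for each volunteer's salvinorin A-minus-air difference in mean frame-to-frame head displacement, computed from the BOLD series already acquired.
3. Present adjusted and unadjusted results side by side. State that an association that disappears on adjustment cannot be distinguished from motion, without making survival of adjustment a decisive test.

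The cost is a few sentences and no new data. If motion is unrelated to the score, the loss is one degree of freedom: power at a true r of 0.6 goes from about 84% to 81%. If movement marks a real drug response the loss is larger, as shown in the working, and larger still with ranks. That is the reason for reporting both versions.
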